9.2.2 Timing

All variables are defined in Appendix 2.

Baseline variables:

- Sex
- Date of birth

The CLASSIC trial protocol Page 28/82

- Date of admission to hospital
- Date and time of admission to ICU
- From where was the participant admitted to ICU
 - o Emergency department or directly from the pre-hospital setting
 - Hospital ward
 - Operating or recovery room
 - Another ICU
- Focus of infection:
 - o Pneumonia
 - o Gastrointestinal infection
 - Urinary tract infection
 - Skin or soft tissue infection
 - Other
- Co-morbidities:
 - o Active hematologic cancer
 - History of metastatic carcinoma
 - History of ischemic heart disease or heart failure
 - History of chronic hypertension
 - o Chronic dialysis
- Blood values, interventions and vital parameters:
 - Participant weight
 - o Highest plasma lactate value within the last 3 hours of randomisation
 - Highest dose of noradrenaline within the last 3 hours of randomisation
 - o Volumes of IV fluid within the last 24 hours of randomisation
 - o Use of systemic corticosteroids in the last 24 hours of randomisation
 - Highest plasma creatinine value within the last 24 hours of randomisation
 - Use of acute renal replacement therapy in the last 3 days prior to randomisation
 - Habitual plasma creatinine value prior to current hospitalisation (mark estimated or measured)
- Values for the Simplified Mortality Score (SMS score)[43] at ICU admission not covered by the above:
 - Lowest measured systolic blood pressure in the last 24 hours prior to randomisation
 - Respiratory support within the last 24 hours of randomisation (support during surgery excluded)

Daily during ICU admission (day form):

- Fluid input and output
 - Total volume and specific type of IV isotonic crystalloids (isotonic saline and buffered solutions: Ringer's lactate, Ringer's acetate and PlasmaLyte™)
 - o Total volume of other IV fluids
 - Total volume of albumin
 - Total volume of fluids with medications
 - Total volume of fluids with nutrition
 - Total volume of blood products

The CLASSIC trial protocol Page 29/82

- Urinary output on this day (ml)
- Total volume of other losses on this day including drainage, aspirates, stools and bleeding
- Did a major protocol violation occur on this day?
- Use of infusion of vasopressor or inotrope on this day
- Use of systemic corticosteroids on this day
- Use of mechanical ventilation on this day
- Use of renal replacement therapy on this day
- Plasma concentration of creatinine

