10.2 Statistical methods

The analyses will be done in the intention-to-treat (ITT) population defined as all randomised participants for whom there is consent for the use of data. We will perform the primary analyses adjusted for the stratification variables [45] and challenge the primary result in analyses adjusted for important baseline risk factors (co-morbidities, higher SMS score, and focus of infection (other foci vs. urinary tract infection)[43, 46] and use of corticosteroids, which may reduce the time in ICU and thus the time exposed to the protocol [47]) and analyses of subgroups (Table 2) and the per-protocol population being the ITT population except those having one or more major protocol violations as defined below (Table 3). If there is more than 5% missing data for outcomes and/or covariates, we will impute the missing data using multiple imputations as described below (10.2.4).

All analyses will be 2-tailed and we will use Fisher's exact test for unadjusted comparisons of dichotomized outcomes (mortality at 90-days and 1-year, SAEs and SARs) and logistic regressions for adjusted analyses of these outcomes. The remaining secondary outcomes are continuous measures; we expect that these are highly skewed (non-normally distribution), because of inflation of specific values such as zero for days alive outside hospital for all patients who die while at the ICU. We will use statistical methods that can accommodate this type of data; the precise models will be specified in the detailed statistical plan.

Several of the secondary outcome measures are composite; we will also analyse each component of these outcomes as recommended [42]; the precise models will be specified in the detailed statistical plan.

Table 2. Heterogeneity of the intervention effects on the primary outcome will be analysed in the following subgroups based on baseline characteristics

Subgroup	Definition	Expected direction of	Statistical test
		the interaction	
Participants who are mechanically ventilated	Invasive mechanically ventilated (yes/no)	Larger effect of fluid restriction in mechanically ventilated participants	Test of interaction in the adjusted analysis described above; P- value 0.01

The CLASSIC trial protocol Page 32/82

Participants with	KDIGO (creatinine)	Larger effect of fluid	Test of interaction in
severe acute kidney	criteria of 2 or above	restriction in acute	the adjusted analysis
injury	[41] (yes/no)	kidney injury	described above; P-
			value 0.01

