 - Acute myocardial ischemia defined as participant with acute myocardial infarction (STelevation myocardial infarction or non-ST elevation myocardial infarction) or unstable
 angina pectoris according to the criteria in the clinical setting in question (e.g. elevated
 biomarkers, ischemic signs on ECG and clinical presentation) AND the participant
 received treatment as a consequence of this (reperfusion strategies (PCI/thrombolysis)
 OR initiation/increased antithrombotic treatment).
 - Intestinal ischemia defined as ischemia verified by endoscopy OR open surgery OR CTangiography.
 - Limb ischemia defined as clinical signs AND need of open/percutaneous vascular intervention, amputation OR initiation/increased antithrombotic treatment.
 - A new episode of severe acute kidney injury defined as modified KDIGO3 [41]: a 3.0 times increase in baseline p-creatinine, or increase in p-creatinine to ≥354 μmol/L, or use of renal replacement therapy (any form) in participants who did not receive this before randomisation.
- -Serious adverse reactions: total number of SARs and number of SARs per participant in the ICU. Serious adverse reactions are defined below.

The CLASSIC trial protocol Page 49/82

- -Number of days alive without life support at day 90: will be assessed from the use of life support including vasopressor/inotrope, mechanical ventilation and renal replacement therapy as defined in the inclusion criteria, baseline and daily variables. Total number of days alive without all of the 3 life supporting interventions within 90 days after randomisation.
- -Days alive and out of hospital at day 90: will be assessed from the discharge date from the index hospitalisation, the number of days readmitted to hospital (if any) and date of death, if relevant, within the 90-day period
- -1-year mortality: landmark mortality 1-year post-randomisation. If the participant has deceased, date of death will be registered.

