Original statistical analysis plan

Version 1.0, published in July 2019.

Conservative versus Liberal fluid therapy in Septic Shock (CLASSIC) trial – statistical analysis plan

The trial protocol and statistical analysis plan were published prior to conducting the interim analyses.¹ All data analyses in the primary publication will be conducted according to this statistical analysis plan except for the changes outlined below.

Coordinating investigator

[name], Department of Intensive Care, Copenhagen University Hospital, Copenhagen, Denmark. E-mail: [contact]

Trial statistician

[name], Section of Biostatistics, University of Copenhagen, Copenhagen, Denmark. E-mail: [contact]

Trial sponsor

[name], Department of Intensive Care, Copenhagen University Hospital, Copenhagen,

Denmark. E-mail: [contact]

Protocol registration numbers

ClinicalTrials.gov identifier: NCT03668236 Ethics committee number: H-18006255 EudraCT number: 2018-000404-42 Danish Medicines Agency number: 2018020596

Trial design

The CLASSIC trial is an investigator-initiated, pragmatic, international, parallel-grouped, centrally randomised, stratified, analyst-blinded trial with adequate allocation sequence generation and allocation concealment.

Trial conduct

The protocol has been prepared according to the Standard Protocol Items: Recommendations for Interventional Trials (SPIRIT) guidelines.² The trial will adhere to this protocol, the Helsinki Declaration in its latest version,³ the international guidelines for good clinical practice (GCP)⁴, and the national laws in the participating countries.

Randomisation

Eligible patients fulfilling all inclusion criteria and no exclusion criteria are randomised 1:1 using a centralised web-based system according to a computer-generated allocation sequence list, the stratification variables and varying block sizes. The allocation sequence list and block sizes are only known by the data manager at Copenhagen Trial Unit, and remain concealed from the investigators until the last patient has completed follow-up.

Blinding

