Sensitivity analyses:

A two-tailed logistic regression analysis adjusted for the stratification variables, the SMS-ICU¹⁴ focus of infection (other foci versus urinary tract infection)^{14,16} and use of corticosteroids¹⁷
 A two-tailed logistic regression analysis in the per-protocol population adjusted for the stratification variables

4. Two-tailed logistic regression analyses in the pre-planned subgroups adjusted for the stratification variables

We will report absolute and relative risk ratios with 95% CIs for the primary analysis of the primary outcome (analysis 1) (P-value <0.05), computed using glm-models with appropriate link functions and binomial error-distribution. Further, we will report the crude event rates in each group and a Kaplan-Meier survival curve for the crude data of the primary outcome.

Secondary outcomes

Dichotomous secondary outcomes will be analysed in the same way as the primary analysis for the primary outcome, i.e.:

• SAEs

Two-tailed logistic regression adjusted for the stratification variables in the ITT population

- SARs
 Two-tailed logistic regression adjusted for the stratification variables in the ITT population
- 1-year mortality

Two-tailed logistic regression adjusted for the stratification variables in the ITT population

A Kaplan-Meier survival curve will be reported for the crude data for secondary outcome 1-year mortality.

The remaining secondary outcomes are continuous measures which we expect to be skewed (nonnormally distributed), because of inflation of specific values such as zero for 'days alive outside hospital' for all patients who die while in the ICU. The outcome measures will be analysed as follows:

- Days alive at day 90 without life support
 Generalised linear model or nonparametric test stratified for site in the ITT population
- Days alive and out of hospital at day 90
 Generalised linear model or nonparametric test stratified for site in the ITT population
- HRQoL 1-year after randomisation⁸
 Generalised linear model or nonparametric test stratified for site in the ITT population
- Cognitive function 1-year after randomisation⁹

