Generalised linear model or nonparametric test stratified for site in the ITT population For the generalised linear model we will initially use Poisson distribution, alternatively negative binomial.¹⁸ If the assumptions for Poisson distribution or negative binomial distribution are not met, data will be analysed using the nonparametric Van Elteren test adjusted for site, but no other variables.¹⁹

The following secondary outcome measures are composite; SAEs, SARs, days alive at day 90 without life support. We will report each component of these outcomes in an appendix to the primary publication without P-values due to the lack of adjustment for multiple comparisons. We will report absolute and relative risk ratios with 99% CIs for dichotomous secondary outcomes. For continuous secondary outcomes we will report mean differences with 99% CIs if they are normally distributed and medians with 99% percentile-based bootstrapped CIs for non-normally distributed continuous secondary outcomes (P-value 0.01) due to the multiplicity of these. A detailed definition of the level of significance for the secondary outcomes is available in the supplement to the published statistical analysis plan. ¹

Sample size

Primary outcome

We plan to enrol 1554 (2 x 777) patients to be able to show a 15% relative risk-reduction (RRR) (7% absolute) in the restrictive group on the primary outcome from an estimated 45% 90-day mortality in the standard care group at type 1 and 2 error levels of 5% and 20% respectively, corresponding to a number needed to treat (NNT) of 14 or less. The anticipated relative risk reduction of mortality and the estimated mortality in the control group is based on data from previous RCTs and systematic reviews.^{20–24}

Trial sequential analysis of existing trials (n=8) have shown that less than 15% of the required information size of 3956 patients to detect or reject a 15% RRR in all-cause mortality with lower versus higher fluid volumes has been reached.²⁵

Secondary outcomes

We expect to have the following statistical power for the secondary outcomes based on 2 x 777 participants, a type 1 error level of 1% and a RRR of 15% in the fluid restriction group versus standard care group:

- 50% power for the number of participants with one or more SAEs (control event rate 25% ^{21,22})
- 10% power for the number of participants with one or more SARs (control event rate 5%^{21,22})

- 80% power for the mortality at 1-year (control event rate 55%^{21,22})

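### The SAE model leaves out pre-randomisation and habitual creatinine, although the kidney component is defined largely by creatinine: missed precision of uncertain size, not bias

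*SAP*

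**What the plan says.** The SAP (Statistical analyses, Secondary outcomes) gives the SAE outcome one model: "Two-tailed logistic regression adjusted for the stratification variables in the ITT population". The model with further risk factors (SMS-ICU, focus of infection, corticosteroids) is listed for the primary outcome only, and none of its terms is creatinine.

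The SAE outcome counts participants with at least one ischaemic event (four kinds) or a new episode of severe acute kidney injury. Protocol Appendix 2 (14.2) says the kidney part is met by "a 3.0 times increase in baseline p-creatinine", by an increase to 354 μmol/L or more, or by renal replacement therapy in someone not receiving it before randomisation.

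Protocol 9.2.2 lists "Highest plasma creatinine value within the last 24 hours of randomisation" as a baseline variable, together with habitual creatinine, which is marked as measured or estimated. The SAP's Missing data section puts both in the imputation model.

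For power, the SAP's Sample size section takes "a type 1 error level of 1% and a RRR of 15% in the fluid restriction group versus standard care group" with a control SAE rate of 25%, and states 50%. Protocol 10.1.2 gives the same figure.

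**The concern.** Two of the three kidney limbs are thresholds on creatinine, so renal function at randomisation bears directly on who can cross them. A baseline covariate on the same scale as part of the outcome is a natural candidate for adjustment. The data are already planned, and the SAP treats them as informative for imputation.

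SAEs are one of the trial's two in-ICU harm outcomes. They are tested at 1% and go to the DMSC at the third interim analysis. Power for this comparison is low. A chance imbalance in baseline kidney function would move the estimate, and the planned model has no term to correct for it.

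**Working it through.** **Inputs.** Sample size: "We plan to enrol 1554 (2 x 777) patients". Allocation: "randomised 1:1 using a centralised web-based system". Sidedness: "All analyses will be 2-tailed" (Protocol 10.2). Control rate 25%; a 15% relative reduction gives 0.25 × 0.85 = 21.25%. Alpha 0.01, so z = 2.576. Not in the documents, hence assumed below: the kidney share of SAEs and how well creatinine predicts an SAE.

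**Step 1. The plan's own power figure.** Power = Φ[(d − z·SE0)/SE1].
- d = 0.25 − 0.2125 = 0.0375; mean rate 0.23125
- SE0 = √(2 × 0.23125 × 0.76875/777) = 0.02139
- SE1 = √((0.25 × 0.75 + 0.2125 × 0.7875)/777) = 0.02137
- (0.0375 − 2.576 × 0.02139)/0.02137 = −0.824, so power = 20.5%

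Other test forms at two-sided 1% (unpooled, arcsine, log odds ratio, log relative risk, continuity-corrected) give 18.8% to 20.6%. Other readings also miss 50%: one-sided 1% gives 28.3%, two-sided 5% 41.8%, one-sided 5% 54.3%, and 1554 per group 46.1%. Reaching 50% without adjustment needs about 1678 per group.

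**Step 2. Gain by variance explained.** If a covariate explains a share R² of the outcome variance, the effective sample size is about n/(1 − R²) and the standard error shrinks by √(1 − R²).

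| Assumed R² | SE ratio | Power |
|---|---|---|
| 0 | 1.000 | 20.5% |
| 0.02 | 0.990 | 21.0% |
| 0.05 | 0.975 | 21.8% |
| 0.10 | 0.949 | 23.3% |
| 0.20 | 0.894 | 26.9% |
| 0.30 | 0.837 | 31.5% |

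The stated 50% would need R² = 1 − 777/1678 = 0.54.

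**Step 3. Check by simulation.** Logistic regression, one normal covariate, 4000 trials per row (simulation standard error about √(0.2 × 0.8/4000) = 0.6 points).

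| AUC for the whole composite | R² | Unadjusted | Adjusted |
|---|---|---|---|
| 0.61 | 0.03 | 19.7% | 20.3% |
| 0.70 | 0.09 | 20.0% | 21.9% |
| 0.78 | 0.20 | 19.3% | 25.7% |
| 0.85 | 0.31 | 20.9% | 32.1% |

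**Step 4. Dilution by non-kidney events.** Creatinine may predict kidney events well and ischaemic events not at all. With a kidney-only AUC of 0.81-0.82 and 2000 trials per setting:
- all SAEs renal: composite AUC 0.81, power 21% to 29%
- three quarters renal: AUC 0.74, power 21% to 25%
- half renal: AUC 0.66, power 20.6% to 22.0%

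**Step 5. The outcome definition.** The relation to creatinine need not be monotone. If the reference for the ratio limb is the pre-randomisation value, a high value makes that limb harder to meet and the absolute limb easier. Someone already at or above 354 cannot newly cross it. Chronic dialysis is recorded and is not an exclusion. In a simulation built on the definition, two linear log-creatinine terms added 4 to 10 points of power if patients already meeting the threshold can count as events, and essentially nothing if the requirement for a new episode excludes them. There was no material loss either way.

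**The case against.** The strongest reply is that nothing here is an error. Adjusting for the stratification variables is valid and matches the primary analysis, and the 99% CI already allows for chance imbalance. That stands.

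A reader might infer that the SAE outcome is dominated by creatinine-based injury. The documents give no component rates, the composite includes four kinds of ischaemia, and the kidney part can be met by new renal replacement therapy alone.

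A reader might also take the covariates as measured in everyone and the precision as free. Habitual creatinine is estimated where no value is on record (Appendix 2), which weakens it as a predictor. Extra covariates also count towards the SAP's 5% missing-data rule, which covers data needed for a given analysis.

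A reader who assumes an AUC of 0.80 for the whole composite could equate the gain to about 27% more patients ((1.97/1.75)² = 1.27). That AUC has no source in the documents, and Step 4 shows how quickly ischaemic events dilute it.

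Finally, components are to be reported without P-values, so adjusting the kidney component alone adds no tested power. These points limit the claim and require care over functional form. They do not show harm from adjusting.

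**Conclusion.** The point holds as a modest, optional improvement. The SAE model omits two planned baseline variables closely tied to part of the outcome's definition. The consequence is possible loss of precision in a valid analysis.

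The gain runs from about nil to roughly 22-27% power, and about 32% at an optimistic AUC of 0.85, against about 20% without adjustment. It rests on the assumed kidney share, the assumed prognostic strength, and the reading of a new episode. No value in this range rescues the comparison: in every case shown, power stays well below one half.

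One firmer finding comes with it. The 50% power stated in both documents does not follow from their own inputs, which give about 20%.

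**What to change.** Pre-specify an SAE model that adds, to site and cancer, the highest pre-randomisation creatinine and its ratio to habitual creatinine. Use a flexible form, for example splines of the logs, with indicators for already meeting the KDIGO3 creatinine threshold and for renal replacement therapy or chronic dialysis at baseline. State which creatinine value is the reference for the ratio limb and whether patients already over the threshold can count.

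Report the marginal risk difference and relative risk by G-computation with 99% CIs. The SAP's summary of changes already records this method for the primary outcome's relative risks. It also keeps the result comparable with the strata-only model, which should be reported alongside. For missing habitual values, use the planned estimate or a simple imputation so that no participant leaves the harm analysis.

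Restate the SAE power as about 20% at two-sided 1% in Protocol 10.1.2 and the SAP. If the adjusted model is added after the March 2022 final analyses, label it post hoc and supportive.

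The cost is a short SAP paragraph, slightly more modelling and a few imputed covariate values. No new data are needed.

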- -HRQoL at 1-year (+/- 2 weeks): EQ-5D-5L and EQ-VAS scores (https://euroqol.org/) obtained by survey by mail or phone as chosen by the participant. Non-survivors will be given the worst possible score. If the participant is incapable of answering the questionnaire (e.g. due to cognitive impairment or coma) we will ask proxies to assess HRQoL for the trial participant (proxy point of view) using the questionnaire aimed for proxies. Non-survivors will be given the worst possible score. EQ-5D-5L will be converted to an index value in combination with the EQ-VAS quantitative measure (0-100 points) quantifying self-rated health
- -Cognitive function at 1-year (+/- 2 weeks): the Montreal Cognitive assessment (MoCa) MINI score (or '5-miniute protocol') using the translations of the MoCa full v. 7.1 (http://www.mocatest.org/). The score will be obtained in all survivors by interview as this was recommended to be the test of cognition in a core outcome set for patients with acute respiratory failure following a modified Delphi process involving patients, researchers and clinicians from multiple continents (http://www.improvelto.com/). Non-survivors will be given the worst possible score. The cognitive function score will be conducted before HRQoL to ensure an equal procedure and avoid that patients are disturbed or tired from the HRQoL score.

If the MoCa MINI, which is validated for phone interview [52], has not been released at the time of the first assessment (1-year after randomisation of the first patient), we will adapt the MoCa MINI from the MoCa full v. 7.1.

SARs will be defined as follows:

- -General tonic-clonic seizures: stiffening and/or jerking movements of all 4 extremities in a patient who becomes or is unconscious in the ICU after randomisation
- -Anaphylactic reactions defined as urticarial skin reaction **AND** at least one of the following observed in the ICU after randomisation
 - Worsened circulation (>20% decrease in blood pressure or >20% increase in vasopressor dose)
 - Increased airway resistance (>20% increase in the peak pressure on the ventilation)
 - Clinical stridor or bronchospasm
 - o Subsequent treatment with bronchodilators

The CLASSIC trial protocol Page 50/82

- -Central pontine myelinolysis seen on CT or MRI scan within the 90-day period after randomisation
- -Hypernatremia defined as p-Na > 159 mmol/L on any plasma sample, including point-of-care testing, done in the ICU after randomisation

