Appendix to the CLASSIC trial statistical analysis plan, version 1.0, published in July 2019.

1.	Statistical analyses: significance level for the secondary outcomes
2.	Definitions of pre-planned subgroup analyses
3.	References

1. Statistical analyses: significance level for the secondary outcomes

We applied the methods as suggested by Jakobsen et al. ¹ As a full Bonferoni correction for multiple comparisons may be too conservative, a pragmatic approach is used dividing the pre-specified P-value threshold with the value halfway between 1 (no adjustment) and the number of primary outcome comparisons (Bonferroni adjustment).

As we have 7 secondary outcomes, the threshold for the P-value for these outcomes was calculated as follows:

0.05/ ((7+1)/2)= 0.0125

A full Bonferoni correction would equal a P-value as follows:

0.05/7 = 0.0071

We then chose the significance level of P 0.01 which is between the two corrections.

2. Definitions of pre-planned subgroup analyses

Heterogeneity of the intervention effects on the primary outcome will be analysed in the following subgroups based on baseline characteristics

Subgroup	Definition	Hypothesised direction	Statistical test
Participants who receive respiratory support	Respiratory support within the last 24 hours prior to randomisation(yes/no)	Larger effect of fluid restriction in patients who receive respiratory support	Test of interaction in the adjusted analysis; P-value 0.01
	Definition: Invasive or non- invasive mechanical ventilation including continuous mask CPAP or CPAP via tracheostomy within the last 24 hours prior to randomisation. Intermittent CPAP and high flow nasal cannula oxygen therapy are NOT considered respiratory support		
Participants with severe acute kidney injury	Modified KDIGO stage 2 or above ³ (yes/no)Definition: Modified KDIGO because we don't have urine output available at randomisation.Stage 2: p-creatinine 2.0-2.9*baseline Stage 3: p-creatinine 3.0*baseline or increase in to ≥354	Larger effect of fluid restriction in acute kidney injury	Test of interaction in the adjusted analysis; P-value 0.01

	mmol/l or initiation of RRT		
Participants with severe metabolic failure	Plasma lactate level >4 mmol/l (yes/no)	Larger effect of fluid restriction in severe metabolic failure	Test of interaction in the adjusted analysis; P-value 0.01

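### The SAP starts four bounded or non-count secondary outcomes with Poisson, then negative binomial, and gives no rule for when to leave them for the rank test

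*SAP*

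**What the plan says.** The SAP (Statistical analyses, Secondary outcomes) treats four outcomes as continuous: days alive without life support, days alive and out of hospital, HRQoL at 1 year and cognitive function at 1 year. Each gets the same line: "Generalised linear model or nonparametric test stratified for site in the ITT population". Skewness is expected "because of inflation of specific values such as zero for 'days alive outside hospital' for all patients who die while in the ICU".

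The order of methods is then given: "For the generalised linear model we will initially use Poisson distribution, alternatively negative binomial". The next sentence supplies the fallback: "If the assumptions for Poisson distribution or negative binomial distribution are not met, data will be analysed using the nonparametric Van Elteren test". That test would account for site and nothing else. No diagnostic, threshold, robust standard error or overdispersion correction is specified. Non-normal outcomes are to be reported as medians with bootstrapped 99% CIs.

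Protocol Appendix 2 gives non-survivors the worst HRQoL and cognition scores. On the HRQoL scale it says: "EQ-5D-5L will be converted to an index value in combination with the EQ-VAS quantitative measure", the latter running from 0 to 100. Protocol section 10.2 had left the precise models for these outcomes to the SAP.

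**The concern.** A Poisson model takes the variance to equal the mean, and a negative binomial takes it to grow with the square of the mean and has no upper limit. The two days outcomes stop at 90 and have a spike at or near zero from deaths. The 1-year scores have a spike at the worst value, at an expected control mortality of 55% (Protocol section 10.1.2). The EQ-5D index is not a count at all.

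The difficulty is the lack of a rule for moving from one step to the next. The ordinary response to overdispersion is to go from Poisson to negative binomial and stop, and nothing in the SAP forces the last step to Van Elteren. If the three steps give very different answers on the same data, the conclusion for each of these secondary outcomes depends on where the analyst stops.

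**Working it through.** **Figures the plan gives.** It states no error rate or power for these four outcomes, so only the surrounding inputs can be reproduced.
- Level: 0.05/((7+1)/2) = 0.0125 and 0.05/7 = 0.0071. The SAP appendix concludes: "We then chose the significance level of P 0.01 which is between the two corrections". Two-sided (Protocol section 10.2), so the critical value is z = 2.576.
- Size: 45% vs 38%, two-sided 5%, 80% power. n = [1.960·√(2·0.415·0.585) + 0.842·√(0.45·0.55 + 0.38·0.62)]² / 0.07² = 777 per arm, as stated.

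**Effect used for power.** A 15% relative reduction in mortality: 0.45 × 0.85 = 38.25% at day 90 and 0.55 × 0.85 = 46.75% at 1 year.

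**Assumptions, not in the documents.** Survivor distributions; 30 sites; worst score taken as 0; cognition on 0-30 or 0-15; EQ-5D index on 0-1. Simulations used 777 per arm and 500-1000 runs per scenario. The Poisson and negative binomial fits had no site term.

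**Poisson.** With φ = variance/mean, the model-based Wald statistic has variance about φ under the null, so the false-positive rate is 2[1 − Φ(2.576/√φ)]. A rate of 60% needs φ of about 24.1.

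| Outcome (assumed shape) | Mean | Variance | φ | Poisson false positives: formula / simulated | Neg. binomial power | Van Elteren type I / power |
|---|---|---|---|---|---|---|
| Days out of hospital, 40% zeros | 37.06 | 1215.06 | 32.8 | 65.3% / 67.6% | 0% | 0.8% / 35.7% |
| Days out of hospital, 47% zeros | 35.33 | 1281.35 | 36.3 | 66.9% / 68.4% | 0% | 0.7% / 40.0% |
| Days without life support, 29% zeros | 47.17 | 1560.74 | 33.1 | 65.4% / 64.1% | 0.5% | 0.8% / 38.8% |
| EQ-VAS | 29.06 | 1202.67 | 41.4 | 68.9% / 68.2% | 0% | 0.5% / 67.6% |
| Cognition, 0-30 | 9.83 | 128.73 | 13.1 | 47.7% / 45.3% | 2.1% | 1.1% / 66.9% |
| Cognition, 0-15 | 4.94 | 32.26 | 6.5 | 31.4% / 33.7% | 6.5% | 1.6% / 66.8% |
| EQ-5D index, 0-1 | 0.32 | 0.15 | 0.46 | 0% / 0% | 17% | 0.9% / 64.7% |

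Negative binomial type I error was 0% in every row.

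**Range for the days outcomes.** Varying mortality (40, 45, 50%), the share of deaths with zero days (30-100%) and the survivors' median stay (5 or 20 days) gave 14-52% zeros and φ of 26-42. Poisson false positives were 57-71%. Negative binomial power was 0-5% with estimated dispersion and 6-60% with dispersion fixed at 1. Van Elteren was not rerun over this grid.

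**Upper bound for cognition on 0-30.** With 55% dead at 0 and every survivor at 30, the mean is 13.5 and the variance 900 × 0.45 × 0.55 = 222.75, so φ = 16.5 and the rate is 53%. Other survivor shapes gave φ of 9.0-14.2 and 39-50%.

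**Why negative binomial loses power.** In the first row the fitted dispersion is 4.25. The model variance is 37.06 + 4.25 × 37.06² = 5874, against 1215 observed. Standard errors are therefore √(5874/1215) = 2.2 times too large, and the effective critical value is about 2.576 × 2.2 = 5.7.

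**EQ-5D index.** φ is below 1, so Poisson errs in the opposite direction: power is 17% against 65% for Van Elteren. The estimated dispersion goes to 0, so negative binomial gives the same result.

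**The case against.** The strongest reply is that the SAP already contains the right test and a route to it. With φ near 30, any ordinary check would reject Poisson. A negative binomial with an implied SD of √5874 ≈ 77 days for an outcome capped at 90 should be rejected too. An analyst who follows the fallback sentence then reaches Van Elteren, which behaves well. The statistician is also masked to allocation, and all the simulated distributions are assumptions.

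Much of this stands. A reader might infer that the plan carries a 60% false-positive rate. It does not: that rate requires Poisson to be kept against the SAP's own condition. Nor does 60% apply to all four outcomes, since it is too high for cognition and has the wrong sign for the EQ-5D index. A reader might also infer that the SAP admits its count models will fail. It says only that it expects skewness and inflation at certain values. The near-zero negative binomial power depends on estimating the dispersion.

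The reply does not supply the missing rule. The SAP never says what counts as a failed assumption, and each outcome line leaves the two approaches joined by an unresolved choice. Masking prevents choosing a test by the favoured direction, but a two-sided P-value can be seen without knowing which arm is which.

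**Conclusion.** The point holds for the four continuous secondary outcomes and does not touch the primary outcome. The first-choice models do not suit these variables, and the move to the test that does is left to an unspecified judgement after the data are seen.

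The size is conditional on which step is retained. Poisson would give about 57-71% false positives for the days outcomes and EQ-VAS, about 31-53% for cognition, and too few for a 0-1 EQ-5D index. Negative binomial with estimated dispersion would leave about 0-7% power on the days outcomes, EQ-VAS and cognition, where Van Elteren has about 36-40% (days) and 65-68% (1-year scores).

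The exact figures rest on assumed survivor distributions and on count models fitted without site. The ordering of the three methods on the days outcomes was the same across the mortality levels and zero shares tried for the count models. The documents do not give the EQ-5D value set; if it contains negative values, a Poisson model could not be fitted to the index.

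**What to change.** Delete the Poisson and negative binomial steps. Name the Van Elteren test, stratified by site as the SAP already has it, as the single pre-specified test at 0.01 for all four outcomes. Adding the cancer stratum is optional.

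Report a mean difference with a percentile-bootstrap 99% CI in place of medians. With 55% control mortality at 1 year, more than half the control arm carries the score given to the dead, so the control median of the 1-year scores would simply be that score.

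The cost is SAP wording only: no new data, and no method that the SAP does not already name. The small downside is that the P-value refers to ranks while the estimate is a difference in means, so the two can occasionally disagree; the report should say so.

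The SAP's summary of changes dates the final analyses to March 2022 and does not mention this choice. For any outcome already analysed, the report should therefore state which step was used and on what check.
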